### **13.3. Assessments during the expansion phase**

Once the safety of the combinations is determined, a single arm expansion phase will be initiated to further confirm the safety and assess the clinical benefit of the combination of standard induction chemotherapy with crenolanib.

#### **13.3.1. Safety monitoring during the expansion phase**

During the expansion phase, safety monitoring will be performed for the entire per protocol patient population (defined as those who receive at least one dose of study drug) and in a separate analysis dictated by chemotherapy agent used.

#### **13.3.2. Response Rate Evaluation**

At the expansion phase, the primary end-point is overall response rate. Patients must have received at least one dose of study drug and have at least one bone marrow disease assessment to be included in the complete response rate.

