## 6. STUDY OBJECTIVES

### 6.1. Primary Objective

- To determine the safety and tolerability of crenolanib given sequentially with cytarabine and anthracycline chemotherapy for newly diagnosed FLT3 mutant AML.
- To determine the response rate to induction therapy in newly diagnosed AML subjects with FLT3 activating mutations when crenolanib is given sequentially with standard induction/consolidation chemotherapy, including the rates of complete remission (CR), CR with incomplete blood count recovery (CRi) and partial remission (PR).

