## 8. TREATMENT PLAN

### 8.1. Summary of Treatment

This is a non-randomized, open label, phase II study enrolling newly diagnosed AML subjects with FLT3 activating mutations. Along with chemotherapy, subjects will be treated with crenolanib divided in three divided doses (preferably every 8 h) continuously until they fulfill one of the criteria for study discontinuation (see Section 7.4).

Study subjects, nursing or research staff will complete documentation (i.e patient diary) during induction and first cycle of consolidation to record the date, time and amount (number of tablets) of crenolanib taken and when taken relative to food. While study subjects are hospitalized, medical records, such as Medication Administration Record, may be used to enter data requested. Once subject is discharged from the hospital, they must submit the crenolanib administration documentation as required during induction 1 (and 2 if applicable), consolidation 1 (Appendix III). All subjects will be assessed for efficacy and toxicity.

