## 12. RESPONSE DEFINITIONS

### 12.1. Response Criteria

Response criteria will be adapted from the International Working Group for AML. [9] Responders are newly diagnosed patients receiving study drug who obtain a CR, CRi, or PR, with or without cytogenetic response, hematologic improvements, and morphologic leukemia-free state. Briefly, criteria are as follows:

1. Complete remission (CR):
  - a. Peripheral blood counts:
    - i. No circulating blasts
    - ii. Neutrophil count  $\geq 1.0 \times 10^9/L$
    - iii. Platelet count  $\geq 100 \times 10^9/L$
  - b. Bone marrow aspirate and biopsy:
    - i.  $< 5\%$  blasts
    - ii. No Auer rods
    - iii. No extramedullary leukemia
2. Complete remission with incomplete blood count recovery (CRi):
  - a. Peripheral blood counts:
    - i. No circulating blasts
    - ii. Neutrophil count  $< 1.0 \times 10^9/L$ , or
    - iii. Platelet count  $< 100 \times 10^9/L$
  - b. Bone marrow aspirate and biopsy:
    - i.  $< 5\%$  blasts
    - ii. No Auer rods
    - iii. No extramedullary leukemia
3. Partial remission:
  - a. All CR criteria except:
  - b.  $\geq 50\%$  reduction in bone marrow blast but within 5-25% or
  - c. Marrow blasts  $< 5\%$  with persistent Auer rods
4. Morphologic leukemia-free state:
  - a. Bone marrow:  $< 5\%$  myeloblasts
5. Hematologic Improvement (HI):  
Hematologic response must be described by the number of positively affected cell lines.
  - a. Blast response (B)
    - i. At least a 50% reduction in blast percentage in peripheral blood (if  $> 5\%$ ) or bone marrow

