## 13. STATISTICAL CONSIDERATIONS

### 13.1. Statistical and analytical plans

The statistical analysis of this study will be the responsibility of AROG Pharmaceuticals or its designees. The clinical research physician/scientist and statistician will jointly be responsible for the appropriate conduct of an internal review process for the final study report and any study-related material to be authorized for publication by AROG or its designees. A statistical analysis plan (SAP) will be prepared as a separate document that details the planned analyses and presentation of the study results.

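### Section 13.3.2 gives no clear denominator for the primary overall response rate, and its only inclusion rule, if it governs that rate, can only raise it

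*Combined protocol and SAP*

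**What the plan says.** Section 13.3.2 opens by naming the endpoint: "At the expansion phase, the primary end-point is overall response rate". The next sentence admits only patients who "received at least one dose of study drug and have at least one bone marrow disease assessment to be included in the complete response rate". No other supplied text says who enters a response rate.

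Other sections bear on how to read this:

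- Section 6.1 gives the efficacy objective: "To determine the response rate to induction therapy in newly diagnosed AML subjects with FLT3 activating mutations". The sentence goes on to specify that crenolanib is given sequentially with the chemotherapy, and it lists CR, CRi and PR.
- Section 12.1 defines the numerator: "Responders are newly diagnosed patients receiving study drug who obtain a CR, CRi, or PR".
- Section 13.3.1 uses a dosed set for expansion-phase safety monitoring, the "entire per protocol patient population (defined as those who receive at least one dose of study drug").
- Section 8.1 states: "All subjects will be assessed for efficacy and toxicity".
- Section 13.1 defers detail: "A statistical analysis plan (SAP) will be prepared as a separate document". No such text is among the supplied documents.

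Study drug means crenolanib: section 8.3 contrasts it with chemotherapy, and section 14.5 speaks of tablets. Section 5.8 puts its start at Day 9. Section 8.2.1 allows a +7-day window and requires acceptable liver tests first. Under the definitions in section 4, enrollment needs only assignment to a treatment.

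**The concern.** The two sentences of section 13.3.2 use different terms. Read strictly, the rule covers only the *complete* response rate, and the primary overall response rate has no stated denominator. If the rule is meant for the primary rate, the denominator depends on events after treatment begins. A patient may enroll, start 7+3, and then die, withdraw or never meet the liver criterion before crenolanib. That patient is not counted.

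The marrow condition is also open to two readings. Section 10.1 requires a screening marrow, so read literally the condition removes almost nobody. If the response marrow of Days 14-28 (section 10.3) is meant, dosed patients who die or leave before it are removed as well. Two analysts could follow the text and report different primary results.

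This is a single-arm study, so the response rate is the main efficacy result. Section 13.1.2 sets the projected rate beside 66-69% for chemotherapy alone and 74-76% with midostaurin.

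**Working it through.** **Plan's own precision figure.** Section 13.1.2 gives ±5% for 90% observed in 120 treated patients. The normal-approximation half-width is 1.96 × √(p(1−p)/n).

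- n = 120: 1.96 × √(0.9 × 0.1/120) = 5.4 points, which rounds to the stated ±5. The exact interval for 108/120 is 83.2% to 94.7%.
- n = 72 (the expansion phase): 1.96 × √(0.9 × 0.1/72) = 6.9 points. The exact interval for 65/72 is 81.0% to 96.0%.

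**Direction.** Under section 12.1 a responder must receive study drug, and CR, CRi and PR all need marrow findings. An undosed patient, or one with no response marrow, therefore adds nothing to the numerator. Removing such patients shrinks only the denominator.

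**Size.** Let r be the reported rate and f the fraction excluded. The rate over all who start induction is r(1 − f). The documents do not give f. Assuming 2-5%:

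- r = 90%: 0.90 × 0.98 = 88.2%; 0.90 × 0.95 = 85.5%. The shift is 1.8 to 4.5 points.
- r = 80%: 0.80 × 0.98 = 78.4%; 0.80 × 0.95 = 76.0%. The shift is 1.6 to 4.0 points.

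In whole patients, for 72 in the expansion phase:

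| Excluded | Rule applied | All 72 | Shift (points) |
|---|---|---|---|
| 1 | 64/71 = 90.1% | 64/72 = 88.9% | 1.3 |
| 2 | 63/70 = 90.0% | 63/72 = 87.5% | 2.5 |
| 4 | 61/68 = 89.7% | 61/72 = 84.7% | 5.0 |

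Four of 72 is 5.6%, just outside the assumed range.

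**Is 2-5% reasonable?** Section 13.2.1 cites 10.3% mortality at 28 days in newly diagnosed AML. With a constant daily risk (an assumption), deaths by Day 9 are 1 − 0.897^(9/28) = 3.4%, and by Day 16 they are 1 − 0.897^(16/28) = 6.0%. The expansion phase excludes patients over 70, therapy-related AML and prior MDS, so its early mortality may be lower. Withdrawals and patients who never meet the liver criterion would add to the losses. The range is plausible but is not established by the documents.

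**The case against.** The strongest case for the plan is that a dosed set fits its question. The objective in section 6.1 concerns response when crenolanib is given, section 12.1 limits responders to patients receiving it, and section 13.3.1 already uses a dosed set for safety. Moving to everyone who starts 7+3 is partly a choice of a different estimand. This stands in part, and it is a reason to report a dosed-patient rate as well. It does not justify dropping dosed patients who lack a response marrow, and it does not repair the mismatch of terms.

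The sentence in section 8.1 is weak support for a wider denominator. It closes a paragraph on dosing records and describes assessment, without setting an analysis set.

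The excluded group may also be small. Section 7.1 item 7 times the liver tests before crenolanib, and the Appendix IV induction key foresees screening during induction chemotherapy. Some patients may thus enroll only after surviving part of 7+3. This limits the likely size of the effect but not its direction.

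The statement that exclusion can only raise the rate depends on section 12.1. An undosed patient who remits on 7+3 alone has responded to induction in the ordinary sense, but is not a responder under that definition.

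Finally, the separate SAP may settle the matter. It was not supplied, so its content is unknown. Sections 13.4 and 13.8 would make discontinuations and deaths visible, but they would not change the rate.

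**Conclusion.** The point holds as a defect of specification with a known direction and an unknown size. The primary rate has no unambiguous denominator. The one rule available, if applied to it, inflates it. With 2-5% excluded, all non-responders, a reported 90% corresponds to 88.2% to 85.5% of those who start induction 1. That shift is smaller than the ±6.9-point sampling half-width at 72 patients. It is a systematic error in one direction, but no decision rests on a threshold.

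Three stronger readings are tempting, and the documents do not support them:

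- A reader might infer that the plan definitely excludes pre-crenolanib losses from the primary rate. The rule literally names only the complete response rate, so this is a likely reading, not a stated one.
- A reader might infer that four exclusions use up the plan's whole ±5% margin. That margin is quoted for 120 patients, whereas the 5.0-point shift is for 72, where the half-width is 6.9 points.
- A reader might infer that the comparison with 66-69% and 74-76% is biased in favour of crenolanib. The denominators behind those figures are not given, so the net bias cannot be established.

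**What to change.** - Use one endpoint term, CR+CRi+PR, in both sentences of section 13.3.2, and state that the marrow must be post-baseline.
- Report the primary rate over all enrolled expansion patients who start induction 1. Count early death, no crenolanib dose or no post-baseline marrow as non-response.
- Because the objective is conditional on crenolanib being given, also report the rate over all dosed patients, with a missing response marrow counted as non-response.
- Keep the dosed-and-assessed set as a sensitivity analysis, with the number of and reason for each exclusion.
- Give the precision for the number of patients actually analysed.

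Separately, the timing of inclusion 7 must be reconciled, so that it is clear who counts as enrolled. The synopsis gives no time, section 7.1 refers to the start of crenolanib, and the Appendix I checklist refers to induction chemotherapy.

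The cost is a few sentences in the protocol and SAP and one extra table. The reported rate will be slightly lower, and an undosed patient who remits on 7+3 alone will count as a non-responder. The wider denominator cannot recover patients lost before enrollment.

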### **13.4. Subject Disposition**

A summary of patient disposition will be provided for each cohort and will include the following:

- Number of patients enrolled
- Number of patients who participate in each study phase (induction, consolidation, maintenance)
- Reasons for discontinuation from study treatment and follow-up
- Summary of major protocol violations

### **13.5. Subject Characteristics**

Patient characteristics will be reported for each cohort, and will include a summary of the following:

- Demographics
- Baseline disease characteristics
- Pre-existing conditions

Other characteristics will be summarized as deemed appropriate.

### **13.6. Concomitant Therapy**

Concomitant medication will be reported overall as well as summarized in a frequency table using the terms recorded on the CRF. If warranted, an attempt may be made to determine how concomitant medications are related to observed study outcomes.

### **13.7. Response Outcome and Methodology**

Response criteria will be adapted from the International Working Group for AML, as stated in section 12.1.

### **13.8. Safety Analyses**

All subjects will be evaluable for safety. Adverse events that occur after a subject is entered (signs informed consent), but before the patient receives study drug, will not be recorded on the CRF unless the investigator believes that the events may have been caused by a protocol procedure. Safety analyses will include summaries of the incidence of adverse events by maximum CTCAE

grade (version 4.03; NCI 2010) that occur during the study treatment period or within 30 days of the last dose of study treatment or until alternate therapy is started, regardless of causality or relatedness to study drug. The safety-related outcomes that will be summarized include:

- Adverse events,
- TEAEs,
- SAEs,
- Deaths,
- Discontinuations due to adverse events,
- Extent of exposure to study drug treatment,
- Hospitalizations,
- Use of key concomitant medications.

Analyses for data with discrete dates (for example, death date and start/stop dates of concomitant medications) will be performed through 30 days after the patient has been discontinued from study treatment or until alternate therapy is started. Adverse events will also be analyzed in this time frame. After 30-day post-discontinuation follow-up, only those SAEs that are thought to be related to study treatment or protocol procedure should be reported immediately to AROG or its designee. For these events, the patient must be followed until the event has resolved or stabilized.

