Enroll	The act of assigning a patient to a treatment. Patients who are enrolled in the trial are those who have been assigned to a treatment.
Investigator	A person responsible for the conduct of the clinical trial at a trial site. If a trial is conducted by a team of individuals at a trial site, the investigator is the responsible leader of the team and may be called the principal investigator.
Institutional Review Board/Ethical Review Board (IRB/ERB)	A board or committee (institutional, regional, or national) composed of medical and nonmedical members whose responsibility is to verify that the safety, welfare, and human rights of the patients participating in a clinical trial are protected.

Legal Representative	An individual, judicial, or other body authorized under applicable law to consent on behalf of a prospective patient, to the patient's participation in the clinical trial.
Patient	A study participant who has the disease or condition for which the investigational product is targeted.
Screen	The act of determining if an individual meets minimum requirements to become part of a pool of potential candidates for participation in a clinical trial. In this study, screening involves invasive or diagnostic procedures and/or tests (for example, radiology and blood draws). For this type of screening, informed consent for these screening procedures and/or tests shall be obtained.
Treatment-Emergent Adverse Event (TEAE)	Any untoward medical occurrence that either occurs or worsens at any time after treatment baseline and which does not necessarily have to have a causal relationship with this treatment (also called treatment-emergent signs and symptoms [TESS]).
ALT	alanine aminotransferase
AML	acute myeloid leukemia
Ara-C	cytarabine
ASCO	American society of clinical oncology
AST	aspartate aminotransferase
BMA	bone marrow aspiration
BUN	blood urea nitrogen
CALGB	cancer and leukemia group b
CBC	complete blood count
CIV	continuous intravenous therapy
CNS	Central nervous system
CR	complete response
CRi	complete remission with incomplete blood count recovery
CYP3A4	Cytochrome P450 3A4
DNA	deoxyribonucleic acid
ECOG -PS	Eastern Cooperative Oncology Group performance status
EFS	Event free survival
EKG	Electrocardiogram
FLT3	FMS-like Tyrosine Kinase 3
GCP	good clinical practice

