#### **14.4. Adverse Event Reporting**

AROG has standards for reporting AEs that are to be followed regardless of applicable regulatory requirements that may be less stringent. Lack of drug effect is not an AE in clinical trials, because the purpose of the clinical trial is to establish drug effect.

Adverse Events (AEs) will be evaluated according to CTCAE version 4.03 and documented in medical record. After the Informed Consent Document (ICD) is signed, study site personnel will record the occurrence and nature of each patient's pre-existing conditions, including clinically significant signs and symptoms of the disease. During the study, site personnel will record any change in the pre-existing condition(s) and the occurrence and nature of any new adverse events.

All AEs related to protocol procedures are reported to AROG or designee. All AEs occurring after the patient receives the first dose of study drug must be reported to AROG or its designee via CRF. Investigators will be instructed to report to AROG or its designee their assessment of the potential relatedness of each AE to protocol procedure, studied disease state, study drug, and/or drug delivery system via CRF.

For all AEs, the investigator should specify:

1. ***Seriousness:*** Seriousness of an AE is defined by the criteria described in Section 10.1. A severe AE should not always be considered as serious.
2. ***Date of onset and its duration (start and end dates):*** The investigator should follow up the outcome of any AEs until they return to normal or consolidation of the subject's condition. All adverse events still evolving at the end of the study are to be followed up by the investigator until their resolution or stabilization.
3. ***Severity:*** (using NCI CTCAE v.4.03),

4. **Action taken with respect to study drug:** (no action taken; study drug dosage adjusted/temporarily interrupted; study drug permanently discontinued due to this adverse event; hospitalization/prolonged hospitalization), corrective treatment/therapy given, additional investigations performed
5. **Outcome:** Resolved/Recovered, recovering/resolving, not recovered/resolved, recovered/resolved with sequelae, unknown
6. **Relatedness:** If an AE is related or not related to study drug

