### **14.5. Serious Adverse Event Reporting**

Serious adverse event collection begins after the patient has signed informed consent and has received a tablet or more of study drug. If a patient experiences an SAE after signing informed consent, but prior to receiving study drug, the event will NOT be collected unless the investigator feels the event may have been caused by a protocol procedure.

In case of a SAE, the investigator, within 24 hours of learning of the SAE or subject death, must notify the sponsor (Arog Pharmaceuticals by e-mail: [contact] or [contact]) and transmit the following information (within a signed SAE report form):

- Subject identification code, demographics and vitals
- Description of event with onset and duration (with CTCAE event term & severity)
- Dates, dose and frequency of study drug administered
- Assessment of the seriousness and causality of the event with the study drug using the causality criteria (EVCTM): related versus not related
- Study drug status (dose interrupted or discontinued)
- Date of death (if applicable)
- Concomitant therapy and interventions
- Pertinent laboratory data/diagnostic tests
- Pertinent medical history including underlying diagnosis

All SAEs must be followed by the investigator until resolution or stabilization until the subject's death. This may mean that follow-up will be extended beyond the subject's withdrawal from the trial. The investigator must provide follow-up information (outcome, more precise medical details, results of investigations, copy of discharge summary, etc...) within 24 hours of information becoming available to Arog Pharmaceuticals and to the study monitor, again using the SAE Report Form indicating follow-up. When this information is passed on, care must be taken to continue to respect subject anonymity. The study monitor may contact, or visit the investigator, in order to obtain details of the event.

The sponsor will report all SUSAR to the country specific regulatory authorities within the request period. The evaluation of expectedness is based on knowledge of the adverse reaction on the reference document: the current reference document is the latest version of the Investigator's Brochure of crenolanib.

The sponsor will also inform the IRB of any SAE with the potential to modify the benefit/risk ratio of the present study. The sponsor will be responsible for reporting of New Safety Issues and Annual Safety Reports to IRBs.

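### Section 13.8 makes all subjects evaluable for safety, but routine AE collection starts only at the first crenolanib dose, so never-dosed patients would dilute AE incidence

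*Combined protocol and SAP*

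**What the plan says.** Section 13.8 opens with "All subjects will be evaluable for safety". It attaches no dosing condition and treats a subject as entered once consent is signed. The following sentence keeps AEs that arise before crenolanib off the CRF, except for those that the investigator thinks a protocol procedure could explain.

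The collection rules follow the same line:

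- Section 14.4: "All AEs occurring after the patient receives the first dose of study drug must be reported to AROG or its designee via CRF". AEs related to protocol procedures are reported as well.
- Section 14.5, on an SAE after consent but before study drug: "the event will NOT be collected unless the investigator feels the event may have been caused by a protocol procedure".

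Section 13.3.1, and the synopsis under its safety analysis heading, use a different population for expansion-phase safety monitoring. They call it per protocol, "defined as those who receive at least one dose of study drug".

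Enrolment does not require a dose. Section 4 says: "Patients who are enrolled in the trial are those who have been assigned to a treatment".

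In the text available for review, no place defines a single safety analysis set or reconciles these statements.

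**The concern.** Safety and tolerability is the first primary objective, and incidence of AEs by maximum CTCAE grade is its main summary. A percentage of this kind is sound only if everyone in the denominator was observed for the events in the numerator. Section 13.8 read literally breaks that condition. The denominator opens at consent, while routine event collection opens at the first tablet.

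Never-dosed patients are foreseeable under this design. Section 5.8 puts the start of crenolanib at Day 9. Sections 1 and 8.2.1 require normal bilirubin, and ALT and AST within limits, in the 24 hours beforehand, and allow the start to be delayed. Section 13.2.1 cites a 28-day mortality of 10.3% in newly diagnosed AML, and some such deaths could fall before Day 9. Section 13.3.2 itself requires at least one dose for the response analysis, which shows that dosing was not taken for granted.

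The error has one direction: toxicity is understated. The denominator could also end up being chosen after the data are seen. The point concerns the final AE, TEAE and SAE tables, not the enrolment-halting counts.

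**Working it through.** **Inputs**

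- Planned enrolment: 24 in Cohort A, 24 in Cohort B and 72 in the expansion phase (synopsis). 24 + 24 + 72 = 120, which reproduces the stated total.
- Illustrative incidences among dosed patients, p: 20% (the grade 4 expected-toxicity threshold in Section 13.2.2) and 50% (the diarrhea rate in Section 8.6).
- Never-dosed share, f: not given in the documents. Assumed range 0% to 20%.
- The plan states no AE incidence or safety-set size, so there is no planned figure of that kind to reproduce.

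**Formula**

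Let q be the incidence, among never-dosed patients, of the events that are still recorded (those a protocol procedure may have caused). With all subjects in the denominator,

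reported incidence = p(1 − f) + q·f.

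The reported figure is below p whenever q is below p. With q near zero it becomes p(1 − f). With a dosed-only denominator it is p.

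**Results with q = 0 and 120 patients**

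| f (assumed) | Never dosed | Dosed | p = 20% reported as | p = 50% reported as |
|---|---|---|---|---|
| 0% | 0 | 120 | 20.0% | 50.0% |
| 5% | 6 | 114 | 0.20 × 0.95 = 19.0% | 0.50 × 0.95 = 47.5% |
| 10% | 12 | 108 | 0.20 × 0.90 = 18.0% | 0.50 × 0.90 = 45.0% |
| 20% | 24 | 96 | 0.20 × 0.80 = 16.0% | 0.50 × 0.80 = 40.0% |

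The relative understatement equals f for every event type.

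**Scale against sampling error**

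The 95% Wald half-width for 20% of 120 is 1.96 × √(0.20 × 0.80 / 120) = 7.2 points. The shift at p = 20% is 0 to 4 points, so it lies inside sampling error over the whole assumed range. It is nevertheless systematic, and more patients would not reduce it.

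**The rules side by side**

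| Place | Who or what | Starting point |
|---|---|---|
| 13.8, first sentence | All subjects evaluable for safety | Entry at consent |
| 13.8, second sentence; 14.4; 14.5 | AEs and SAEs collected routinely | First crenolanib dose |
| Synopsis; 13.3.1 | Expansion-phase safety population | First crenolanib dose |

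Two of the three rows agree. The opening sentence of Section 13.8 is the one that does not fit.

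**The case against.** **All subjects may mean all treated subjects.** Section 13.8 limits AE summaries to the treatment period and 30 days after the last dose. Section 4 counts TEAEs from treatment baseline, and Section 10.2 places baseline on the first day of crenolanib. A never-dosed patient has neither a crenolanib baseline nor a last crenolanib dose. Section 13.8 also never says in so many words that incidence is divided by all subjects. This reading is possible and would match Section 13.3.1. But nothing states it, and the only entry point that Section 13.8 names is consent.

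**Detail is deferred.** Section 13.1 promises a separate SAP, which might define a safety set. No such definition appears in the text available. An SAP written from this protocol would still start from a sentence that conflicts with the collection rules.

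**The effect may be nil.** Section 7.1 times the liver criterion to just before crenolanib, and the Appendix IV induction key contemplates screening during induction chemotherapy. Both could keep f small. The Appendix I checklist times the same criterion to before induction, so f remains unknown. Safety is reported descriptively, and a reader given both enrolment and exposure could probably recalculate. These points limit the importance of the problem but do not resolve the conflict.

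**Two stronger readings are not supported.** A reader might infer that safety-phase figures follow Section 13.8, expansion figures follow Section 13.3.1, and the two phases are therefore not comparable. Section 13.8 is the general safety analysis for the whole study, and Section 13.3.1 concerns monitoring, so the documents do not assign a different reporting denominator to each phase. A reader might also infer that never-dosed patients are event-free by rule. They are not: procedure-related events are recorded before dosing, and deaths are a separate outcome, with Section 14.8 covering all deaths during the study.

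**Conclusion.** The point holds as an internal conflict with a predictable direction. Section 13.8 makes everyone evaluable for safety from consent, while routine event collection starts at the first crenolanib dose, and the synopsis and Section 13.3.1 use a dosed-only population. Followed literally, Section 13.8 understates every AE incidence by about the never-dosed share. The size rests on an assumed f and on few recorded pre-dose events among never-dosed patients. The bias is zero if every subject is dosed, and at f = 20% a 20% incidence is reported as 16%. This is worth correcting because it affects the main readout of a primary objective, but nothing in the documents shows that the distortion will be large.

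**What to change.** In Section 13.8, replace the opening sentence with: *AE, TEAE and SAE incidence is calculated in all patients who received at least one dose of crenolanib, in both phases.* This matches the population in Section 13.3.1 and the synopsis. Carry the same definition into the SAP.

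In Section 13.4, add to the disposition summary the number enrolled but never given crenolanib, with the reasons and any deaths among them, so that these patients remain visible after leaving the AE denominator.

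The cost is a sentence in each section and no new AE collection. If the CRF does not already capture why crenolanib was never started, it needs a field for that. AE percentages may be slightly higher than under the all-subjects wording. If the sponsor prefers to keep all subjects as the denominator, AE and SAE collection would have to begin before crenolanib, which is a larger change.
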